specialized and primary - during transition, amplifying existing barriers to accessing crucial services as disease burden is increasing. 20,21 A retrospective study showed that patients who are transitioning received 46% fewer transfusions by age 22y compared to children and were 4.7 times less likely to receive iron chelation by age 25y. 21 At Atrium Health (formerly known as Carolinas Healthcare System), a large healthcare system in the SE US that provides care for 1300 adults and 400 children with SCD, only 8-14% of EA-SCD accessed a scheduled visit with their primary care/SCD provider in 2015 with mean acute care reliance (ACR; number of acute care visits per year/ [all acute care visits + all ambulatory care visits]) rates of 42% (Fig 2). Mean acute care visits/year rose significantly from 2.1 ± 2.9 among 16- 18y to 4.2 ± 6.8 among 19 - 21y and was highest among 21 - 25y at 5.3 ± 8.5 (p<0.01). ACR (\geq 0.33) is an indicator of inadequate access to primary and preventative care. 22 EA-SCD report having inadequate information about adult care and a poor understanding of their disease and how it becomes more complex with age. $^{14, 16}$ There are significant knowledge gaps and poor communication between pediatric and adult providers that worsen the problem created by a lack of standardized EA-SCD patient education curriculum.

Limited evidence on effective transition programming:

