10.2 Sample Size and Accrual

Sample size calculations are based on the primary endpoint of acute care utilization visits per year (at the EA-SCD participant level). Utilizing a randomized cluster design, seven clinical sites will be randomized per arm. The sample size calculation strategy is to calculate the required minimum sample size based on an individual patient randomized design, and then inflate the sample size based on cluster randomized considerations.⁵⁴ A conservative estimate of the average acute care utilization rate for EA-SCD is 6 acute care visits per year based on data for North Carolina reported by the RuSH population surveillance project.⁴ In South Carolina, the acute care utilization rates among 18-30 y with SCD was reported as 7.17 (95% CI 6.34-7.99).55 At Atrium Health (formerly known as Carolinas Healthcare System), 295 EA-SCD had 1972 emergency department visits and 221 hospital admissions in 2015 with an average acute care

utilization rate of 6.82 visits per year. This study is designed to detect a 20% reduction in the number of acute care encounters per year (assuming a base case of 6 encounters). A 20% reduction in acute care utilization is considered clinically significant based on patient partners reporting that 1 less acute care visit a year is meaningful. Based on a two- sided alpha = 0.05significance level, 67 EA-SCD participants per arm would provide approximately 85% power to detect a 20% reduction in the number of acute care utilizations under individual randomization, assuming the number of encounters follows a Poisson distribution for rare events. The sample size will be inflated based on two parameters: the cluster size coefficient of variation and the intra-class correlation (ICC).⁵⁴ The cluster size coefficient of variation observed among the 14 participating clinical sites is 55%. Therefore, the coefficient of variation is assumed to be 60% and the ICC is assumed to be 0.05.⁵⁶ Based on these parameters, a minimum of 183 EA-SCD participants per arm (366 total EA-SCD participants) will retain approximately 85% power. To account for potential missing data and allow for robust evaluation of secondary endpoints the sample size will be increased to a total of 537 EA-SCD participants. It is estimated that this enrollment can be accomplished with an enrollment rate of 35% of the EA-SCD patient population.

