10.5.4 Primary Analysis

To evaluate the impact of PM, the acute care utilization rate per year will be compared between the PM+STE and STE arms. This will be accomplished using generalized linear mixed model with a Poisson distribution-log link construct. The model will include fixed effects for baseline acute care visits per year, the stratification factor (large sites vs small sites) and treatment arm, and a random effect for clinical site. Corresponding 95% confidence intervals will be calculated for the estimated ACU rate in each treatment arm.

Supportive and sensitivity analyses will be conducted to include potential confounding factors such as urban versus rural sites, education level, older first degree relative with SCD, genotype, age at transfer to adult care, and type of receiving provider (primary versus specialty). Univariate models will be fit for each factor, and those identified to be individually prognostic will be included in a multivariable model, and backward elimination followed by forward selection will be used to identify factors that are independently prognostic and to establish a final base model. Finally, treatment arm will be added to the base model to evaluate the impact of the intervention adjusting for significant baseline factors.

Two analyses will be conducted to estimate the impact of differential accrual between arms over time: (1) An additional term of year of enrollment will be added to the GLMM as a categorical variable; (2) We will subset the analyses to EA-SCD who were contemporaneously enrolled. Comparison of the PM+STE and STE ACU estimates from this subset to those results including all enrolled with and without controlling for year of enrollment will provide a comprehensive assessment of the potential bias due to differential accrual between arms over time. ACU rate in the STE only arm will be compared to historical ACU rates which were used for the original power calculations. Although these are comparisons to historical controls, this will provide preliminary evidence using a robust sample size of the potential impact of the structure transition education.

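### The stated 85% power at 366 participants holds only for Poisson visit counts; the protocol's own spread figures are 4 to 14 times wider in variance, and the plan neither allows for this nor checks it

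*Combined protocol and SAP*

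**What the plan says.** Section 10.2 starts from an individually randomised comparison of 6 against 4.8 visits per year, "assuming the number of encounters follows a Poisson distribution for rare events", and obtains 67 per arm. It then inflates for clustering: "Therefore, the coefficient of variation is assumed to be 60% and the ICC is assumed to be 0.05". The result is that "a minimum of 183 EA-SCD participants per arm (366 total EA-SCD participants) will retain approximately 85% power". The further increase to 537 is attributed to missing data and secondary endpoints. The synopsis repeats the claim but shows only the observed cluster-size CV of 55%.

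Section 1.1 reports yearly acute care visits in one participating health system, rising "from 2.1 ± 2.9 among 16- 18y to 4.2 ± 6.8 among 19 - 21y" and "highest among 21 - 25y at 5.3 ± 8.5".

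Section 10.5.4 specifies a "generalized linear mixed model with a Poisson distribution-log link construct". "The model will include fixed effects for baseline acute care visits per year"; the list goes on with the site-size stratum "and treatment arm, and a random effect for clinical site". It names no dispersion or participant-level term, and does not say on what scale baseline visits enter. Sections 8.2 and 10.5.1 provide for ongoing checks of the cluster-size CV and the ICC.

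**The concern.** A Poisson count has variance equal to its mean. The spreads in Section 1.1 are far larger, which is what one expects when a few patients account for many visits. The sample-size calculation inflates for clustering but makes no allowance for extra variation between participants, and it takes no credit for baseline adjustment either. The monitoring does not list dispersion, so the gap could stay unnoticed.

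This is the headline power for the primary endpoint. If it is too high, a null result would be read as stronger evidence against a 20% reduction than the trial can give.

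**Working it through.** **Inputs.** From 10.2: rates 6 and 4.8, two-sided alpha 0.05, 7 sites per arm, CV 0.60, ICC 0.05, 183 per arm. Planned enrolment of 537 is 268.5 per arm. From 1.1: the three mean ± spread pairs, with ± read as SD (if it were a standard error, the dispersion would be larger still).

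**1. The plan's figure.** Individual randomisation: n = (1.96 + 1.036)² × (6 + 4.8)/1.2² = 67.3. Fixed number of clusters: 67 × 0.95/(1 − 67 × 0.05 × 1.36/7) = 182.3, hence 183. With CV 0.55 the same formula gives 169, so 183 rests on the 60% that the synopsis omits. Check: design effect 1 + (183 × 1.36/7 − 1) × 0.05 = 2.73; SE² = 10.8 × 2.73/183 = 0.161; power = Φ(1.2/0.401 − 1.96) = 84.9%. The arithmetic is sound.

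**2. Dispersion in Section 1.1.** Variance/mean: 2.9²/2.1 = 4.0; 6.8²/4.2 = 11.0; 8.5²/5.3 = 13.6. As negative-binomial dispersion, k = (SD² − mean)/mean² = 1.43, 2.38, 2.38. The document does not say which of the two carries over to a mean of 6, so both are used. Carrying k gives one-year variances of 57.5 and 91.7, or 9.6 and 15.3 times the mean. Carrying the lowest ratio gives 24.

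**3. Power with 24 months of follow-up and baseline adjustment.** Let V1 be the one-year variance, ρ the year-to-year correlation of the participant effect, and cov = ρ(V1 − mean). The variance of the 24-month mean rate is v24 = (V1 + cov)/2, and r = cov/√(V1 × v24). Then

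SE² = [sum over arms of v24(1 − r²)]/n + 2 × (site variance) × 1.36/7.

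Site variance is first held at the plan's Poisson value, 0.05 × 5.4 = 0.27, so the second term is 0.105. Against V1 of 24 to 91.7, that implies an ICC of only about 0.01 to 0.003.

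- Ratio 4, r = 0.7, n = 183: 0.51 × (19.6 + 15.7) = 18.0; SE² = 0.098 + 0.105 = 0.203; power 76%.
- k = 1.43: 0.51 × (46.9 + 30.8) = 39.6; SE² = 0.217 + 0.105 = 0.322; power 56%.
- k = 2.38: 0.51 × (74.8 + 48.7) = 63.0; SE² = 0.344 + 0.105 = 0.449; power 43%.

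| Case | 366, r = 0.7 | 537, r = 0.7 | 366, fully stable | 537, fully stable |
|---|---|---|---|---|
| Ratio 4 | 76% | 82% | 81% | 86% |
| k = 1.43 | 56% | 67% | 79% | 85% |
| k = 2.38 | 43% | 54% | 79% | 85% |

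Fully stable means ρ = 1, which gives r of about 0.80, 0.92 and 0.95 in the control arm.

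**4. ICC kept at 0.05 of the larger variance**, 366, r = 0.7. Ratio 4: site variance 0.05 × (24 + 19.2)/2 = 1.08; SE² = 0.098 + 0.420 = 0.518; power 39%. k = 2.38: site variance 0.05 × (91.7 + 59.6)/2 = 3.78; SE² = 0.344 + 1.470 = 1.814; power 14%.

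**5. Fourteen sites.** Replacing 1.96 by the t(12) reference lowers the plan's own Poisson power from 85% to 78% at 366, and from 89% to 83% at 537.

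**The case against.** The strongest reply is that the model adjusts for baseline visits, which may remove most of the spread. This largely stands as a reason not to name one corrected power. If baseline explained all site variance as well, the second term of SE² would vanish. At 366 and r = 0.9, the participant sums for k = 1.43 and 2.38 are 16.9 and 26.9, giving SE² of 0.092 and 0.147 and power of 98% and 88%. But the plan states neither r nor that assumption, and its calculation uses no baseline credit.

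A reader might infer that the unstated scale of baseline visits alone decides the matter. In simulations of the planned model at 537 (k 1.43-2.38, z test), r = 0.9 gave 52-75% with untransformed baseline and 92-98% with log(visits + 0.5). Those runs let baseline and follow-up share the same site effects. Without that, log baseline gave only 78-83% even with a fully stable spread. Scale matters, but not alone.

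A reader might also infer that the Poisson model is invalid and a negative-binomial model is required. That is not shown. At k = 2.38 with log baseline and t(12), simulated power at r = 0.7, 0.8 and 0.9 was 51, 66 and 90% for the planned model, and 41, 47 and 64% for the negative binomial. No type I error was obtained for the planned model in that setting. In a separate, smaller simulation the planned model's z test rejected a true null in 6.5-13.5% of runs, but already in 8.5-10% without any overdispersion. That points mainly to the small number of sites, and the site random effect absorbs much of the excess variance.

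Other points that stand: the SDs are unadjusted and come from one system with means of 2.1 to 5.3. Section 8.2 does name design assumptions as a monitoring goal. The synopsis says the peer-mentoring comparison cannot be assessed quantitatively as intended, which lowers the risk of misreading. The unqualified 85% nevertheless remains in 10.2 and the synopsis.

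**Conclusion.** The 85% at 366 is conditional on a Poisson variance that the protocol's only spread figures contradict. It is not reached in any case in steps 3 and 4: 43-76% at r = 0.7 and 79-81% with fully stable differences when site variance is held at 0.27, and 14-39% at r = 0.7 when the ICC stays at 0.05. At 537 the range with site variance 0.27 is 54-82% at r = 0.7, and 85-86% only if participant differences are fully stable. These figures assume ± is SD, a mean of 6, 24 months for everyone and a normal reference.

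They are a range, not a corrected power. The low figures should not be read as the trial's true power, because r and the ICC convention are unknown and a log-scale baseline that also explains site differences could exceed 85%. Nor does the point imply a need for more participants. With ICC 0.05 and ratio 4, unlimited enrolment at 14 sites would still leave SE² = 0.42, and so power of about 46%.

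**What to change.** 1. In 10.2 and the synopsis, restate power and the detectable reduction as a range. Use the Section 1.1 dispersion, stated baseline correlations, the ICC convention chosen and a t reference for 14 sites. Give the assumed CV of 60% in the synopsis.
2. In 10.5.1, add to the CV and ICC checks the dispersion of the 12-month baseline visits, which are already collected, and their correlation with follow-up, both pooled over arms.
3. In 10.5.4, state the scale on which baseline visits enter and use a small-sample reference for the arm test. Choose a dispersion-robust or participant-level term only after its simulated type I error and power have been compared with the planned Poisson model; do not mandate a negative-binomial model.

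Cost: wording, one recalculation and a little more analysis work. The stated power becomes less favourable. No new data or participants are needed.

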10.3 Endpoints

10.3.1 Definition of Primary Endpoint

Acute care visits will be calculated for each EA-SCD participant as the average number of acute care visits over a24-month period. Acute care visits will also be calculated for each EA-SCD participant as the average number of acute care visits per year over the entire study as a secondary endpoint. Acute care visits may include, but are not limited to hospital admissions, ED, urgent care, day hospital, or infusion center visits. The calculations for these endpoints are below:

$$Months \ on \ study = \frac{(Off \ Study \ Date - Enrollment \ Date)}{30.4375}$$

$$Acute \ care \ visits \ per \ 24 \ months = \frac{Total \ \# \ acute \ care \ visits \ reported \ on \ study}{Months \ on \ study} * 24 \ months$$

$$Acute \ care \ visits \ per \ 12 \ months = \frac{Total \ \# \ acute \ care \ visits \ reported \ on \ study}{Months \ on \ study} * 12 \ months$$

10.3.2 Definition of Secondary Endpoint

Quantitative EA-SCD participant-reported outcome scores will be captured longitudinally for each subject. Data will be collected for each subject using the following scales:

- Adults Sickle Cell QOC Measure (ASCQ-ME QOC) for health-related quality of life
- PedsQLTM-SCD module for health-related quality of life
- Medical Outcomes Study Social Support Survey (MOS-SSS)
- Transition Readiness Score as measured by the TIP-RFT scale
- Health Care Transition Feedback Survey

Count variables capturing healthcare utilization will be calculated for each EA-SCD participant for the following variables. These will be annualized to 12-month and 24-month periods as described above.

- The number of ambulatory visits
- The number of visits with adult providers
- The number of hospitalization days
- 14-day and 30-day readmission rates

10.3.3 Definition of Intervention Fidelity (PM Intervention Feasibility) Endpoint

- The number of consented mentor candidates that complete each step of eligibility and training activities (i.e., background check, practice call 1, PMU training, practice call 2, match with EA-SCD)
- Timelines for major milestones for Mentors
 - o Time from consent to background check result
 - o Time from background check result to practice call 1
 - o Time from practice call 1 to completion of PMU training
 - Time from completion of PMU training to practice call 2 (enrollment/completion of training activities)
 - Time from practice call 2 to first match with EA-SCD (postenrollment)
- Time from first consent date to enrollment for EA-SCDs on the PM arm
- Frequency of mentor-mentee contacts via the platform

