3.6 Screen Failures

A consented subject who, for any reason (e.g., failure to satisfy the eligibility criteria or withdraws consent for study participation), terminates his/her study participation before enrollment (as defined in section 10.1) is regarded as a "screen failure." All screen failures will be recorded in the ST3P-UP Study REDCap database.

The Sponsor Investigator requests sites to also record pre-screen failures through REDCap. Pre-screen failure is defined as a subject that did not sign informed consent but was considered for potential study participation.

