- Should a mentor be consented, but not initiate training within 30 days and/or complete training within 60 days of consent, he/she will be deemed a screen fail.
- Should a mentor consent to study but fail to be enrolled within 90 days consent or reconsent he/she will be deemed a screen fail.
- Reconsent will be obtained according to Advarra IRB's policy.
- •Advisors will be assigned mentors based on an advisor:mentor ratio of up to 1:5 at any point in time, and mentorship will continue until the end of study. Advisors will communicate with their mentors at least once monthly through the platform. The study EDC platform will track the number of assigned mentors to each advisor and only add an additional mentor when review of advisor ratio is under the maximum allowed of 1:5.
 - Should a mentor go off study prior to end of study, the advisor will have availability to be assigned a new mentor.
 - Should an advisor go off study prior to end of study, the mentors assigned to that advisor will be reassigned to another advisor.
 - If an advisor is unable to continue with their study related activities, an alternate advisor will be recruited.
 - Should an advisor be consented to study, but not initiate training within 30 days and/or complete training within 60 days of consent, he/she will be deemed a screen fail.
 - Should an advisor consent to study but fail to be enrolled within 90 days of consent or reconsent, he/she will be deemed a screen fail.
 - Reconsent will be obtained according to Advarra IRB's policy.

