10.1.2 Enrollment Date

EA-SCD Participants:

The date the baseline survey is administered to a subject (either within a healthcare setting or via survey link).

For participants on the PM arm, administration of the baseline survey and completion of the enrollment CRF occurs after confirmation of mentor matching from the DCC (see study calendar 6.3).

Mentor and Advisor Participants:

The date the participant completes all training activities. For mentors, this is the date the participant completes practice call 2. For advisors, this is the date the participant completes Peer Mentor University training.

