10.4 Analysis Populations

All EA-SCD participant-level analyses will be conducted on the population of all enrolled EA-SCD participants (consented EA-SCD participants who are enrolled per section 10.1.2), regardless of how long the EA-SCD participant was on study or regardless of the extent of data missingness.

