10.5.5 Secondary Analysis

EA-SCD PRO's will be analyzed quantitatively using linear mixed models for repeated measures. The models will include fixed factors for baseline scales, the site size stratification factor, treatment arm, assessment time point, and the treatment arm by time point interaction. Random factors will include investigational site and subject within site to account for correlation in responses within individual sites and within the same subject. Model-based estimates of PRO scores will be used to estimate percentage change between the treatment arms. Additionally, PRO will be analyzed using survival analysis techniques. For each EA-SCD participant, the time from baseline to a 10% worsening (TTW) in the scale will be calculated. For EA-SCD participants not experiencing a 10% worsening, TTW will be censored at the last patient reported outcome assessment. TTW will be analyzed using Kaplan-Meier techniques and Cox proportional hazards models. The

proportional hazards models will include the same factors as described for the primary analysis. Planned sensitivity analysis will be conducted to evaluate time to worsening for worsening thresholds ranging from 10% to 30%. The repeated measures and survival analyses of the EA-SCD PRO's will also include supportive and sensitivity analyses to account for potential baseline confounders as previously described in the primary analysis. EA-SCD satisfaction with transition services will be summarized descriptively.

Intervention fidelity will be analyzed descriptively. A CONSORT-type diagram will be provided, including a summary of all mentors who consented, had a background check, passed the background check, completed practice call 1, completed Peer Mentor University online training, completed practice call 2, and were matched with at least one EA-SCD. Timelines for mentors and EA-SCDs on the PM arm will be summarized descriptively. Frequency of mentor contacts will be analyzed descriptively in terms expected contacts per protocol versus actual. This will include calls placed (mentor to EA-SCD), calls answered (EA-SCD to mentor), messages sent (mentor to EA-SCD), and messages received (EA-SCD to mentor).

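### On the PM arm the consent-to-enrollment wait is summarized only for participants who were matched and enrolled, so it understates the true wait

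*Combined protocol and SAP*

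**What the plan says.** Section 10.3.3 defines the participant wait as "Time from first consent date to enrollment for EA-SCDs on the PM arm". Its last mentor interval is "Time from practice call 2 to first match with EA-SCD (postenrollment").

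Section 10.1.2 makes a match, confirmed by the data coordinating center, a condition of enrollment on this arm: "For participants on the PM arm, administration of the baseline survey and completion of the enrollment CRF occurs after confirmation of mentor matching from the" (the sentence goes on to name that center). The calendar notes in 6.3 likewise require a match before the baseline surveys.

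Section 10.4 sets the population: "All EA-SCD participant-level analyses will be conducted on the population of all enrolled EA-SCD participants". It makes no exception for the waiting-time endpoint.

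The method, in 10.5.5, is one sentence: "Timelines for mentors and EA-SCDs on the PM arm will be summarized descriptively". No denominator, censoring rule or competing event is given. The same section does give a censoring rule for time to worsening of the patient-reported outcomes.

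For mentors, 5.2.3 limits the time to starting and completing training (30 and 60 days from consent) and to enrollment: "Should a mentor consent to study but fail to be enrolled within 90 days consent or reconsent he/she will be deemed a screen fail".

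Non-completion is recorded elsewhere. Section 3.6 states that "All screen failures will be recorded in the ST3P-UP Study REDCap database", and 10.3.3 counts "The number of consented mentor candidates that complete each step of eligibility and training activities". Section 10.5.5 adds a mentor flow diagram from consent to match, and 10.5.2 starts the participant CONSORT diagram from all those consented.

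**The concern.** A waiting time that exists only for people whose wait ended in success is a conditional quantity. People who give up, lose eligibility or are still waiting at study close tend to have the long waits. Leaving them out pulls the summary down, and more so as matching gets slower.

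The protocol expects such delays. Inclusion criterion 8 in 3.2.1 provides for reconsent when matching is late and requires the participant to remain eligible from the reconsent date, so a long wait can itself lead to exclusion. At stake is how a reader judges whether mentors can be supplied in time. A short median wait could be reported although many consented participants never obtained a mentor.

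**Working it through.** **Plan's own figure.** The documents give no target wait, expected match rate or precision for these endpoints, so there is nothing to reproduce.

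**Who has a value (participants).** The endpoint needs an enrollment date (10.3.3). On the PM arm that date needs a confirmed match (10.1.2). Only enrolled participants are analyzed (10.4). A consented, unmatched participant therefore has no value and is outside the population as well.

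**Who has a value (mentors).** Section 10.3.3 lists five intervals. The first four run from consent to practice call 2, which is the mentor's enrollment date. Their sum is bounded by the 60- and 90-day limits, with the 90-day clock restarting at reconsent. The fifth, practice call 2 to first match, comes after enrollment, so those limits do not bound it. It is undefined for a mentor never matched. Section 10.4 speaks only of EA-SCD participants, so the mentor population is unstated.

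**Illustration 1: withdrawal and study close.** These inputs are assumptions, not document figures: exponential time to match with median M, exponential withdrawal with median D of 6 or 12 months, and time to close uniform on 0 to 24 months. With λ = ln 2/M, μ = ln 2/D and a = λ + μ:

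- Share matched: p = (λ/a) × [1 − (1 − e^(−24a))/(24a)].
- Median among the matched: the x at which the integral of λe^(−at)(1 − t/24) from 0 to x equals p/2.

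For M = 6 and D = 6: λ = μ = 0.1155, a = 0.2310, 24a = 5.545, so p = 0.5 × (1 − 0.996/5.545) = 0.41. The median is solved numerically.

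| True median M (months) | Share matched (D = 6; D = 12) | Median among matched, months (D = 6; D = 12) |
|---|---|---|
| 0.5 | 90%; 93% | 0.45; 0.47 |
| 1 | 81%; 87% | 0.81; 0.87 |
| 3 | 59%; 69% | 1.8; 2.0 |
| 6 | 41%; 51% | 2.4; 3.0 |
| 9 | 31%; 40% | 2.8; 3.5 |

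**Illustration 2: a single cut-off C.** The share finishing is F = 1 − e^(−λC), and the median among finishers is −ln(1 − F/2)/λ. With C = 12 months (assumed):

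- M = 60 days: 99% matched, median reads 59 days.
- M = 90 days: 94% matched, reads 82 days.
- M = 180 days: 76% matched, reads 123 days.
- M = 365 days: 50% matched, reads 152 days.

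With C = 90 days, the length of the mentor enrollment limit, true medians of 90 and 180 days read as 37 and 41 days.

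In both models the median among finishers lies at or below the true median, and the gap widens as the share matched falls.

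**The case against.** A reader might infer that failed matching is hidden and that the whole feasibility result is biased. The documents do not support that. Mentor completions are counted step by step, including the match. There is a mentor flow diagram from consent, and the participant CONSORT diagram starts from consent and gives withdrawals with reasons. In Illustration 1 the share matched falls from 59–69% to 31–40% as the true median rises from 3 to 9 months, so a reader who sets the counts beside the times would notice. This stands in large part. What remains is that 10.5.2 does not name matching as a step, and a count does not correct a biased duration.

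A reader might also infer that the 60- and 90-day limits truncate the mentor matching time. They do not, because that interval starts after enrollment. Nor does the plan say that mentor times are restricted to completers; it is silent.

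Three further points stand:

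- Counting from the first consent keeps the full delay of participants who were reconsented and later matched. It does nothing for those never matched.
- The sizes rest wholly on assumed rates, and with fast matching little bias is left.
- The benchmark M is a latent wait with no withdrawal, which a cumulative incidence does not estimate. With match and withdrawal medians both 6 months and no study close, cumulative incidence at 6 months is 0.5 × (1 − 0.25) = 37.5%, not 50%. The illustrations show the direction and possible scale of the problem, not an error that the fix would remove number for number.

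Finally, these are descriptive items under a secondary objective (2.2.3), with no threshold or test.

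**Conclusion.** The point holds in a limited form. As written, 10.1.2, 10.3.3, 10.4 and 10.5.5 together give a participant waiting time conditional on being matched, which understates the wait. The mentor interval from practice call 2 to first match is likewise undefined for mentors never matched.

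The direction follows from the definitions; the size cannot be known from the documents. Under the assumed exponential times, the median is about 7 to 10% too short when about 90% are matched (0.45 to 0.47 against 0.5 months). When 41 to 51% are matched, it is about 40 to 50% of a true 6-month median.

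The primary analysis is not touched, and non-completion is reported separately. This is a cheap improvement to a descriptive endpoint, not a threat to the trial's main conclusions.

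**What to change.** Exempt the consent-to-enrollment endpoint from the enrolled-only rule in 10.4. In 10.5.5, specify:

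- **Participants:** cumulative incidence of enrollment at fixed times (for example 1, 3, 6 and 12 months) for all consented PM-arm participants, from first consent. Withdrawal or screen failure is a competing event, and those still waiting are censored.
- **Mentors, matching:** the same display for first match among all trained mentors, from practice call 2. Leaving the study unmatched is the competing event, and those still waiting are censored.
- **Mentors, earlier steps:** show the times beside the step counts and note the 30-, 60- and 90-day screen-fail limits. State whether the consent clock starts at first consent or reconsent.
- **All intervals:** give the number contributing.

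The cost is a little more analysis and SAP wording. Consent dates and screen failures are already captured. However, 7.1 waives the end-of-study form for people who consented, were not enrolled and withdrew, and 3.6 promises a screen-failure record without mentioning an exit date. Some exit dates may therefore have to be taken from the research chart. No new visits or participants are needed.
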